6.4 Treatment of Study Drug Overdose

For this study, accidental or intentional oral ingestion of drug product will be considered an overdose. Ingestion of a 30-gram tube of tapinarof cream, 1% would result in an oral dose of 300 mg.

The Sponsor does not recommend specific treatment for an overdose; however, in the event of an overdose, the Investigator (or treating physician) should do the following:

- Contact Medical Monitor to discuss the event
- Closely monitor the subject for AEs/SAEs and laboratory abnormalities
- Provide general symptomatic treatment as necessary
- Document the quantity of the excess dose as well as the duration of the overdosing.
- If the Medical Monitor requests a plasma sample for PK analysis, then a blood sample for PK should be obtained within 2 days from the date of the last dose of study drug.

Decisions regarding dose interruptions or modifications following an overdose will be made by the Investigator in consultation with the Medical Monitor based on the clinical evaluation of the subject.

6.5 Pharmacokinetics

Blood samples for PK analysis of tapinarof cream, 1% will be collected at timepoints indicated in the Schedule of Assessments ([Table 1](#)) and Section 7. Blood samples for PK should not be collected from any anatomic site where study drug has been applied in order to minimize potential contamination. The actual date and time of each blood sample collection will be recorded as well as the date and time of the last dose of study drug prior to sample collection. Collection, processing, storage, and shipping procedures are provided in the Study Reference Manual or Laboratory Manual.

Concentrations of tapinarof will be determined in plasma samples using a validated bioanalytical method. Raw data will be archived at the bioanalytical site. From the plasma concentration time data on Day 1, the following primary PK parameters will be determined: $AUC_{0-\text{last}}$, C_{max} , t_{max} , and t_{last} .

An analysis of the PK data will be performed after 25% of the subjects (n=9) have completed the study to reassess the PK sampling scheme with the potential to eliminate the 5-hour post-dose blood draw. If required, changes to the protocol will be made through a protocol amendment.

6.6 Virtual Assessments

In the event that a subject cannot attend their regularly scheduled study visits in person due to a COVID-19-like situation necessitating a limit on in-person contact, the Investigator may perform safety and efficacy assessments by phone or video. Source documentation should note if the visit was performed by phone or video. The Investigator may use the technology platform that is currently available to them. Suggested platforms include Apple FaceTime, Zoom for Healthcare, Facebook Messenger video chat, Microsoft Teams, Google Hangouts video, and Skype. Additional details should be included in source documentation, as detailed in the Study Reference Manual.

If the subject can only be contacted by phone, the following should be assessed or performed:

- AEs
- Concomitant Medications
- Reminder to complete diary
- Instruction not to discard empty tubes of study drug

If the subject or caregiver has video capabilities, the following items should be assessed or performed:

- AEs
- Concomitant Medications
- vIGA-AD™ assessment (excluding subject's scalp)
- %BSA affected calculation (excluding subject's scalp)
- EASI (excluding subject's scalp)
- LTS (Investigator assessment)
- Application of study drug by the subject
- Completion of the PP-NRS itch scale – The subject can verbally indicate the answer which the study coordinator will document in the source document.
- Reminder to complete diary
- Instruction not to discard empty tubes of study drug

The reason that assessments cannot be completed during a virtual assessment (i.e., labs, vital signs, physical exams, etc.) must be noted (e.g., COVID-19) and the missed assessments will be recorded as protocol deviations.

7 Timing of Procedures and Assessments

This section lists the procedures and assessments to be performed at scheduled timepoints during the study as outlined in the Schedule of Assessments ([Table 1](#)). Information on study procedures and assessments is provided in Section [6](#).

- Any change in timing or any addition of a timepoint(s) for any planned study assessment must be documented in a “Note to File,” which is approved by the relevant Sponsor study team member and then archived in the study Sponsor and site study files; this will NOT constitute a protocol amendment.
- The IRB/IEC will be informed of any safety issues that require alteration of the safety monitoring scheme or amendment of the ICF.

NOTE: Assessments and procedures should be performed pre dose on clinic visit days.

7.1 Visit 1; Screening Period (Day -30 to Day -1)

After the subject has signed the consent/assent form, potential study subjects will undergo Screening procedures and assessments to confirm eligibility to participate in the study. Screening assessments will include the following:

- Demography recording
- Fitzpatrick skin type
- Brief physical examination (including height and weight [BMI will be calculated in the CRF])
- Medical history recording (including all medications up to 30 days prior to screening and all systemic [oral and injectable] medications used by the subject for the treatment of AD prior to 30 days before screening)
- Serum pregnancy test (females of child-bearing potential)
- Blood sample collection for clinical laboratory tests (serum chemistry, hematology, diagnostic tests)
- Urinalysis
- Vital signs measurements
- Blood sample collection for PK analysis (if the subject is eligible)
- AE recording (from the time the ICF is signed)
- Concomitant medication recording (including emollients)
- vIGA-AD™ score (excluding subject’s scalp)
- %BSA affected calculation (excluding subject’s scalp)

To determine subject eligibility at Screening, a single repeat of tests or procedures may be allowed at the discretion of the Investigator. The Medical Monitor should be consulted if needed.

7.2 Visit 2; Baseline (Day 1)

On Day 1, subjects will be reassessed to confirm continued eligibility to participate in the study. All subjects who continue to meet study eligibility criteria will be enrolled and receive treatment.

The following additional procedures and assessments will be performed at the Baseline Visit:

- Brief physical exam
- Changes to medical history
- Urine pregnancy test (females of child-bearing potential)
- Vital signs measurement
- Dispense study drug
- Provide instructions on how to apply study drug
- Dispense study drug subject diary and PP-NRS diary
- Study drug application under supervision
- Blood sample collection for PK analysis
- AE recording
- Concomitant medication recording
- vIGA-AD™ score (excluding subject's scalp)
- %BSA affected calculation (excluding subject's scalp)
- EASI (excluding subject's scalp)
- LTS assessment by Investigator
- Assessment of itch (PP-NRS)

7.3 Visit 3; Week 1 (Day 8 ±2 Days)

The following procedures and assessments will be performed at Visit 3:

- Brief physical exam
- Vital signs measurement
- Collect and dispense study drug
- Review instructions on how to apply study drug
- Collect study drug subject diary and PP-NRS diary and review for compliance
- Dispense study drug subject diary and PP-NRS diary
- Study drug application under supervision
- AE recording

- Concomitant medication recording
- vIGA-AD™ score (excluding subject's scalp)
- %BSA affected calculation (excluding subject's scalp)
- EASI (excluding subject's scalp)
- LTS assessment by Investigator
- Assessment of itch (PP-NRS)

7.4 Phone Contact at Day 15 ±2 Days

Subjects or their caregivers will be contacted by phone at Day 15 to review instructions on how to apply study drug and to record AEs and concomitant medication use. Subjects should be reminded to complete their daily diary and bring it with them to the next clinic visit.

7.5 Visit 4; Day 28 ±2 Days

The following procedures and assessments will be performed at Visit 5:

- Brief physical exam
- Urine pregnancy test (females of child-bearing potential)
- Blood sample collection for clinical laboratory tests (serum chemistry, hematology, diagnostic tests)
- Urinalysis
- Vital signs measurement
- Collect study drug
- Collect study drug subject diary and PP-NRS diary and review for compliance
- Blood sample collection for PK analysis
- AE recording
- Concomitant medication recording
- vIGA-ADTM score (excluding subject's scalp)
- %BSA affected calculation (excluding subject's scalp)
- EASI (excluding subject's scalp)
- LTS assessment by Investigator
- Assessment of itch (PP-NRS)
- Enrollment in open-label, long-term safety study (optional)

7.6 Visit 5; Follow-Up (Day 35 ±3 Days)

Subjects who do not enroll in the open-label long-term safety study will return to the study site 7-10 days after Day 28 to complete follow-up assessments as follows:

- Brief physical examination
- If needed, blood sample collection for clinical laboratory tests
- If needed, urinalysis
- Vital signs measurement
- AE recording
- Concomitant medication recording
- vIGA-AD™ score (excluding subject's scalp)
- %BSA affected calculation (excluding subject's scalp)
- EASI (excluding subject's scalp)

7.7 Early Termination Visit

Subjects who withdraw early from the study will be asked to return to the study site to complete Early Termination assessments as follows:

- Brief physical examination
- Urine pregnancy test (females of child-bearing potential)
- Blood sample collection for clinical laboratory tests
- Urinalysis
- Vital signs measurement
- Collect study drug
- Collect study drug subject diary and PP-NRS diary and review for compliance
- AE recording
- Concomitant medication recording
- vIGA-AD™ score (excluding subject's scalp)
- %BSA affected calculation (excluding subject's scalp)
- EASI (excluding subject's scalp)

7.8 Unscheduled Visit

Subjects may have an unscheduled visit for AE follow-up, study drug dispensation, make-up for a missed visit, or other reason. The following assessments may be performed as needed:

- Brief physical examination

- Urine pregnancy test (females of child-bearing potential)
- Blood sample collection for clinical laboratory tests (serum chemistry, hematology, diagnostic tests)
- Urinalysis
- Vital signs measurement
- Dispense and / or collect study drug
- Review instructions on how to apply study drug
- AE recording
- Concomitant medication recording
- Dispense and / or collect subject diaries
- vIGA-AD™ score (excluding subject's scalp)
- %BSA affected calculation (excluding subject's scalp)
- EASI (excluding subject's scalp)
- Assessment of itch (PP-NRS)
- Review subject diaries for treatment compliance

7.9 End of Study

The end of study is defined as when the last active subject has completed the Follow up Visit (if subject does not enroll in the separate open-label, long-term safety study) OR the last active subject has completed the 27 days of treatment in this study (if subject is eligible and enrolls in the separate open-label, long-term safety study).

8 Safety Monitoring and Reporting

8.1 Adverse Events, Serious Adverse Events, and Adverse Events of Special Interest

The Investigator or site staff is responsible for detecting, documenting, and reporting events that meet the definition of an AE, SAE, or adverse events of special interest (AESIs). At each visit/contact, subjects should be questioned in a general way so as not to introduce bias in detecting AEs and/or SAEs. Open-ended and non-leading verbal questioning of the subject is the preferred method to inquire about AE occurrence.

Investigators are not obligated to actively seek AEs or SAEs in former study subjects. However, if the Investigator learns of any SAE, including a death, at any time after a subject has been discharged from the study, and he/she considers the event reasonably related to the study drug or study participation, the Investigator should promptly notify the Sponsor.

A narrative will be written and included in the Clinical Study Report for all SAEs and AESIs, and for all AEs that lead to study discontinuation.

8.1.1 Definition of Adverse Events

An AE is any untoward medical occurrence in a subject temporally associated with the use of a medicinal product, whether considered causally related or not related to the medicinal product.

An AE can therefore be any unfavorable and unintended sign (including an abnormal laboratory finding), symptom, or disease (new or exacerbated) temporally associated with the use of a medicinal product.

Events meeting the definition of an AE include:

- Any abnormal laboratory test results (hematology, clinical chemistry) or other safety assessments (e.g., vital signs measurements), including those that worsen from Baseline, and felt to be clinically significant in the medical and scientific judgment of the Investigator
- Exacerbation of a chronic or intermittent pre-existing condition (e.g., plaque psoriasis) including either an increase in frequency and/or intensity of the condition
- For skin-related AEs, it should be noted whether or not the event is in the area of active application of study drug, and/or if spreading beyond the application site.
- New conditions detected or diagnosed after study drug administration even though it may have been present prior to the start of the study
- Signs, symptoms, or the clinical sequelae of a suspected interaction
- Signs, symptoms, or the clinical sequelae of a suspected overdose of either study drug or a concomitant medication (overdose per se will not be reported as an AE/SAE)
- "Lack of efficacy" or "failure of expected pharmacological action" per se will not be reported as an AE or SAE. Such instances will be captured in the efficacy assessments. However, the signs, symptoms, and/or clinical sequelae resulting from lack of efficacy will be reported as AE or SAE if they fulfill the definition of an AE or SAE.

Events that **do not** meet the definition of an AE include:

Any clinically significant abnormal laboratory findings or other abnormal safety assessments that are associated with the underlying disease, unless judged by the Investigator to be more severe than expected for the subject's condition

The disease/disorder being studied or expected progression, signs, or symptoms of the disease/disorder being studied, unless more severe than expected for the subject's condition

Medical or surgical procedure (e.g., endoscopy, appendectomy); the condition that leads to the procedure is an AE

Situations where an untoward medical occurrence did not occur (social and/or convenience admission to a hospital)

Anticipated day-to-day fluctuations of pre-existing disease(s) or condition(s) present or detected at the start of the study that do not worsen

8.1.2 Definition of Serious Adverse Event

If an event is not an AE per Section 8.1.1, then it cannot be an SAE even if serious conditions are met (e.g., hospitalization for signs/symptoms of the disease under study, death due to progression of disease, etc.).

- An SAE is any untoward medical occurrence that, at any dose:
 - Results in death
 - Is life-threatening
 - The term “life threatening” refers to an event in which the subject was at risk of death at the time of the event. It does not refer to an event, which hypothetically might have caused death, if it were more severe.
- Requires hospitalization or prolongation of existing hospitalization
 - In general, signifies that the subject has been detained (usually involving at least an overnight stay) at the hospital or emergency ward for observation and/or treatment that would not have been appropriate in the physician's office or outpatient setting. Complications that occur during hospitalization are AEs. If a complication prolongs hospitalization or fulfills any other serious criteria, the event is serious. When in doubt as to whether “hospitalization” occurred or was necessary, the AE should be considered serious.
 - Hospitalization for elective treatment of a pre-existing condition that did not worsen from Baseline is not considered an AE.
- Results in disability/incapacity: a substantial disruption of a person's ability to conduct normal life functions.
 - This definition is not intended to include experiences of relatively minor medical significance such as uncomplicated headache, nausea, vomiting, diarrhea, influenza, and accidental trauma (e.g., sprained ankle) which may interfere or prevent everyday life functions but do not constitute a substantial disruption.
- Results in a congenital anomaly/birth defect

Medical or scientific judgment should be exercised in deciding whether reporting is appropriate in other situations, such as important medical events that may not be immediately life-threatening or result in death or hospitalization but may jeopardize the subject or may require medical or surgical intervention to prevent one of the other outcomes listed in the above definition. These should also be considered serious. Examples of such events are invasive or malignant cancers, intensive treatment in an emergency room or at home for allergic bronchospasm, blood dyscrasias, or convulsions that do not result in hospitalization, or development of drug dependency or drug abuse.

8.1.3 Adverse Events of Special Interest

In prior clinical studies, contact dermatitis, folliculitis, and headache have been identified as AEs of particular clinical importance and will be reported as AESIs in this study.

In each case study drug may be continued or discontinued, based on Investigator judgment, and may be restarted when the event resolves. In addition, the following information should be collected for each of these AESIs:

Contact Dermatitis

The study site should collect location, time to onset, duration, size, associated symptoms (itching, burning, pain), severity (mild, moderate, severe), concomitant medications used to treat, action taken with study drug and photograph the affected site (if possible). If the subject contacts the study site to report significant skin irritation at or near the site of study drug application between study visits, the subject should be brought in for an unscheduled visit, if possible.

Headache

The study site should collect time to onset, duration, severity (mild, moderate, severe), location (e.g., frontal, temporal, occipital, diffuse).

Follicular Event

The study site should collect the location, duration, size, associated signs and symptoms (itching, burning, pain erythema), severity (mild, moderate, severe), describe morphology [scale (keratotic/cornified) or no scale (non-keratotic/non-cornified)], time to onset, and photograph the affected site (if possible). Additional information regarding management of folliculitis is provided in Section 8.2.1.2.4.

In particular, the term ‘folliculitis’ may not correctly describe the morphology of the observed local follicular events as these appear to be more consistent with a keratoses pilaris-like follicular based papule. Tapinarof upregulates components of the stratum corneum, including involucrin, hornerin, and filaggrin and increased cornification at, and subsequent mechanical occlusion of, the follicular ostia has been suggested to be a potentially on target mechanism by which these lesions may develop in some individuals treated with tapinarof cream. Additional morphologic description will help to more fully and appropriately characterize these follicular events.

Possible descriptors include, but are not limited to:

- Folliculitis
 - Non-inflammatory

- Inflammatory
- Milia
 - Non-inflammatory
 - Inflammatory
- Keratosis pilaris
 - Non-inflammatory
 - Inflammatory

Additional AESIs may be identified during the evaluation of safety data for the Clinical Study Report.

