4.6.1 Reasons for Withdrawal from the Study

Study drug will be discontinued and the subject will be withdrawn from the study for any of the following reasons:

- Subject has an AE that is considered to be related to study drug or procedures AND is severe enough to warrant treatment discontinuation, as determined by the Investigator (Section 8.1).
- Pregnancy
- Any Grade 3 or 4 AE, based on National Cancer Institute Common Terminology Criteria for Adverse Events (CTCAE) criteria, considered causally related to study drug (Section 8.2.2)

Study drug may be discontinued and the subject withdrawn from the study for any of the following reasons:

- Subject requires concurrent prohibited medication during the study. Nonmedicated emollients that do not contain salicylic acid may be used on nonlesional skin; emollients should not be applied to lesional skin during treatment. The same emollient should be used throughout the subject's participation in the study.

NOTE: If, in the opinion of the Investigator and the study Medical Monitor, such medication will not interfere with the conduct or interpretation of the study or compromise the safety of the subject, then the subject may continue to receive study drug. If the subject is permanently discontinued from study drug, they may remain in the study for safety assessments as needed, at the discretion of the Investigator and Medical Monitor, but they are not eligible to enroll in the open-label, long-term safety study.

- Subject noncompliance

- Investigator noncompliance
- Discontinuation of the study at the request of the Sponsor, regulatory agency, or an Institutional Review Board (IRB)/Independent Ethics Committee (IEC).

If a subject meets a withdrawal criterion during treatment, an Early Termination visit will be required (Section 7.7).

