8.2.1.2.4 Folliculitis

Subjects using tapinarof topically may experience folliculitis. The majority if these events are mild and moderate and do not require intervention or interruption in study drug use. On close inspection, the morphology is similar to that of keratoses pilaris suggesting that the potential mechanism may be increased follicular cornification with subsequent follicular plugging. Importantly, AhR regulates the epidermal differentiation complex and tapinarof has been shown to repair the skin barrier through activation of stratum corneum components including fillagrin, hornerin and involucrin. This latter point suggests that the keratosis pilaris-like reaction may be an on-target effect associated with a therapeutic response to tapinarof cream.

While the majority of events have not required nor resulted in the need for intervention, several approaches can be employed to manage those patients with folliculitis who may be symptomatic including temporary interruption of study drug use at sites of folliculitis and/or the local application to affected areas of topical keratolytics such as 12% lactic acid lotion, 5-10% urea creams or lotions.

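### Section 8.1.3 lets the Investigator continue or restart study drug for the three AESIs with no grade or causality limit, which conflicts with the mandatory withdrawal rule in Section 4.6.1

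*Protocol*

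**What the plan says.** Protocol Section 8.1.3 names contact dermatitis, folliculitis and headache as AESIs and gives one dosing rule for all three: "In each case study drug may be continued or discontinued, based on Investigator judgment, and may be restarted when the event resolves". For contact dermatitis it adds that, when significant irritation is reported between visits, "the subject should be brought in for an unscheduled visit, if possible". Its only pointer to management is for follicular events: "Additional information regarding management of folliculitis is provided in Section 8.2.1.2.4". That section says of folliculitis that "The majority if these events are mild and moderate and do not require intervention or interruption in study drug use", and for symptomatic cases it offers "temporary interruption of study drug use at sites of folliculitis". It states no grade limit either.

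Section 4.6.1 is mandatory: "Study drug will be discontinued and the subject will be withdrawn from the study for any of the following reasons". Two of its reasons matter here. One is "Any Grade 3 or 4 AE, based on National Cancer Institute Common Terminology Criteria for Adverse Events (CTCAE) criteria, considered causally related to study drug". The other has no grade threshold: an AE related to study drug or procedures that the Investigator judges severe enough to stop treatment. The section ends: "If a subject meets a withdrawal criterion during treatment, an Early Termination visit will be required".

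Section 8.2.1.2 sets rules by grade:
- **Grade 1 or 2 (8.2.1.2.1):** continuing is left to the Investigator.
- **Grade 3 (8.2.1.2.2):** a related event should lead to discontinuation. Dosing may continue only with compelling evidence that the drug was not the cause, and after discussion with the Medical Monitor.
- **Grade 4 (8.2.1.2.3):** permanent discontinuation, whatever the cause.

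**The concern.** The two sections give different answers for the same child. An Investigator who continues or restarts drug after a related Grade 3 contact dermatitis is within 8.1.3 and in breach of 4.6.1. Neither section refers to the other.

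The subjects are aged 2 to 17, the study is a maximal-use study with safety as a primary objective, and the protocol itself singles these events out as clinically important. With about 12 sites, different readings could also affect which children are withdrawn, which are counted among TEAEs leading to drug or study discontinuation (SAP Section 13.2), and which can go on to the extension study.

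**Working it through.** This is a consistency check of text, with one small dose count.

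**Step 1: do the grade rules reach AESIs?** Yes. Section 8.2.1.1 has every AE graded by CTCAE, with Table 5 for terms that CTCAE does not cover. SAP Section 13.2 plans to summarise causality, grade and action taken with study drug for AESIs.

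**Step 2: compare the rules case by case.** In every row, 8.1.3 allows the drug to be continued, or stopped and restarted.

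| AESI | 4.6.1 | 8.2.1.2 | Result |
|---|---|---|---|
| Grade 1-2, not judged severe enough to stop | not triggered | Investigator's discretion | no conflict |
| Related, any grade, judged severe enough to stop | stop and withdraw | depends on grade | restart conflicts with 4.6.1 |
| Grade 3, related | stop and withdraw | discontinue | continuing conflicts with both; restart conflicts with 4.6.1 |
| Grade 3, unrelated | not triggered | may continue on two conditions | 8.1.3 only omits the two conditions |
| Grade 4, related | stop and withdraw | permanent stop | conflict on paper with both |
| Grade 4, unrelated | not triggered | permanent stop | conflict on paper with 8.2.1.2.3 |

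In the related Grade 3 row, the bar on restart rests on 4.6.1 alone. Section 8.2.1.2.2 says to discontinue, then speaks separately of Grade 3 events that need a permanent stop, so it does not clearly rule out resuming after recovery.

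**Step 3: dose ceiling per affected child.** Section 3.3 defines intended doses as the study day of the Day 28 visit minus 1, which is 27 if the visit falls on Day 28. If the event is found before dosing on Day d and drug is never interrupted, the doses still open under 8.1.3 are 27 - d + 1.
- Day 8: 27 - 8 + 1 = 20
- Day 15: 27 - 15 + 1 = 13
- Under 4.6.1: 0 in both cases

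The ±2-day window on the Day 28 visit moves the first two figures by up to 2 either way.

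**Step 4: extension eligibility.** A completer needs at least 80.0% of intended doses: 0.80 × 27 = 21.6, so 22 doses (22/27 = 81.5%). A child restarted after missing up to 5 doses could still meet that threshold. Under 4.6.1 the same child is withdrawn and, if this happens before Day 28, cannot enter the extension (Section 3.1). The extension's other entry criteria are in a separate protocol.

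**The case against.** The best defence is that the sections can be read together. Section 8.1.3 is permissive and 4.6.1 is mandatory and universal, and a permission ordinarily operates inside a mandatory limit. Section 11.1.9 holds the Investigator to the whole protocol. Section 8.1.3 mainly lists data to collect, while the dosing rules sit under the toxicity management heading, where the folliculitis paragraph follows the Grade 3 and Grade 4 rules. An Investigator who stops the drug satisfies every section. On this view only a linking clause is missing.

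That reading is sensible and is probably what was meant, but no visible text states it. Section 8.1.3 applies its discretion to each of the three events without qualification, and restarting the drug cannot be squared with withdrawal from the study. Section 1.3.1 (risks) is not in the public text, so it cannot be excluded that something there bears on this.

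The protocol also has safeguards: the unscheduled visit, notice to the Medical Monitor of severe signs that put the subject at risk (8.2.1.2.5), 24-hour SAE reporting, and ongoing team review of safety data (10.5). They make it less likely that a severe case goes unseen, but none of them decides dosing.

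A reader might infer more than the documents support:
- **That Grade 4 AESIs are a practical problem.** Whether these terms reach Grade 4 depends on CTCAE v5.0, which is not reproduced, so this limb stands on paper only.
- **That many children would be wrongly dosed.** No Grade 3 or 4 AESI rate is given. Purely as an assumption, a per-child risk of a related Grade 3 AESI of 0.5%, 1%, 2% or 5% gives a chance of at least one case among 36 of 1 - (1 - p)^36 = 17%, 30%, 52% or 84%. That is the chance that such an event occurs. It says nothing about how often an Investigator would then act on 8.1.3 against 4.6.1.

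**Conclusion.** The conflict is real and should be fixed. Its practical core is the related Grade 3 AESI. There is a second overlap at any grade, where the Investigator judges a related AESI severe enough to stop treatment and 8.1.3 would still allow a restart. It would therefore be too generous to say that Grade 1 and 2 events are wholly untouched. For an unrelated Grade 3 event there is no contradiction over whether dosing may continue; 8.1.3 only leaves out the two conditions.

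Few children are likely to be affected, since the protocol describes most prior events as mild or moderate. The figure of 20 doses against 0 is a ceiling: it assumes discovery before dosing on Day 8, a Day 28 visit on Day 28, and uninterrupted dosing. Sample size is not affected, and no planned analysis needs to change.

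**What to change.** Replace the dosing sentence in 8.1.3 with wording such as: *Subject to Sections 4.6.1, 8.2.1.2.2 and 8.2.1.2.3, the Investigator may continue, temporarily interrupt or discontinue study drug; drug that was temporarily interrupted may be resumed once the event has resolved.* State in 8.2.1.2.4 that the same limits apply to folliculitis.

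The distinction between interruption and discontinuation is needed. A sentence that simply left Grade 1 and 2 events to the Investigator, restart included, would not settle the grade-free reason in 4.6.1.

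The cost is a protocol amendment with IRB/IEC and regulatory submission, and approval before it takes effect (Section 11.2.1). Data collection and SAP outputs do not change.
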